## Sponsor/Quotient Sciences Confidential

Study Day	Screening	Admis-sion	Resident in Clinic												End of Study Visit
			Period 1							Period 2					
	-28 to -2	-1	1	2	3	4	5	6	7	8	9	10	11	12 a	14 b
Prior and Concomitant Medication	< -----X----- >														
PK/Pharmacogenetic Assessments															
Plasma Samples for MMV367 p			X	X	X	X	X		X	X	X	X	X	X	X
Blood Sample for CYP/UGT polymorphism q			X												

Eligibility will be re-assessed at admission/pre-dose on Day 1.

a Discharge from clinical unit

b Participants will return for an end of study visit on Day 14 ( $\pm$  1 day).

c Update only

d Weight only

e It is planned that testing will comprise an antigen test performed at screening and on Day -1 prior to admission to the clinical unit. The definition of the COVID-19 testing time points are subject to change based on the current risk mitigation in place and will be agreed by the study team and documented in the ISF via the Clinical Kick-Off Meeting minutes.

f Participants will be randomised on the morning of Period 1, Day 1 prior to dosing

g Participants will receive a single dose of MMV367 on Day 1 and Day 8 in the fed or fasted state

h Targeted (symptom driven) physical examination of the relevant body system(s) as clinically indicated, as per the investigator's judgement

i Haematology, coagulation, clinical chemistry and urinalysis at each time point, including virology and FSH (post-menopausal female participants only) at screening.

j Post-menopausal female participants only

k All female participants

l See [Appendix 6](#) for single and triplicate 12-lead ECG time points. For triplicate ECGs, participants will be required to rest in the supine position with no external stimuli (e.g. music or television) for 15 min prior to the nominal time point where a triplicate ECG is scheduled.

m Continuous Holter monitoring will commence at least 1.5 h prior to dosing until at least 24 h post-dose. Participants will be required to rest in the supine position with no external stimuli (e.g. music or television) for 15 min prior to the nominal time point where an ECG extraction is scheduled. See [Appendix 6](#) for Holter extraction time points.

n Telemetry (continuous ECG monitoring) will commence at least 30 min before dosing until at least 12 h post-dose.

o Blood pressure, heart rate and respiratory rate at all time points. Oral temperature will be measured at screening and admission only. See [Appendix 6](#) for vital signs time points.

p See [Appendix 6](#) for PK sample time points.

q Sample will be taken prior to IMP administration ( $\leq$ 2 h before dosing).

## Sponsor/Quotient Sciences Confidential

## Appendix 4 Schedule of Assessments: Part 3 (Cohorts 3A to 3C)

Study Day	Screening	Admission	Resident In-clinic							Return Visit b	End of Study Visit b
	-28 to -2	-1	1	2	3	4	5	6	7 a		
General Assessments											
Informed Consent	X										
Medical History	X	X c									
Weight, Height and BMI	X	X d								X d	X d
Vein Assessment	X										
Carbon Monoxide Breath Test	X	X									
Drug Screen	X	X									
Alcohol Breath Test	X	X									
SARS-CoV-2 Antigen e	X	X									
Randomisation f			X								
IMP Administration g			X	X	X						
Safety Assessments											
BDI-II Questionnaire	X	X									
Physical Examination	X	X									
Targeted (symptom driven) Physical Examination h			X	X	X	X	X	X	X	X	X
Safety Labs i	X	X			X		X		X	X	X
Urinalysis i	X	X			X		X		X	X	X
Follicle-stimulating Hormone (FSH) Test j	X										
Serum Pregnancy Test k	X										
Urine Pregnancy Test k		X								X	X
Single 12-Lead ECGs l	X	X	X		X	X					
TriPLICATE 12-Lead ECGs l				X		X	X	X	X		
Holter Periods m			X	X	X	X					
Vital Signs n	X	X	X	X	X	X	X	X	X	X	X
Orthostatic Vital Signs n	X		X	X	X	X				X	
Adverse Events	<-----X----->										
Prior and Concomitant Medication	<-----X----->										
PK/Pharmacogenetic Assessments											
Plasma Samples for MMV367 o			X	X	X	X	X	X	X	X	

**Sponsor/Quotient Sciences Confidential**

Study Day	Screening	Admission	Resident In-clinic							Return Visit b	End of Study Visit b
	-28 to -2	-1	1	2	3	4	5	6	7 a		
Blood Sample for CYP/UGT polymorphism p			X							9	17

Eligibility will be re-assessed at admission/pre-dose on Day 1.

a Discharge from clinical unit

b Participants will return for an outpatient visit on Day 9 and an end of study visit on Day 17 (± 1 day).

c Update only

d Weight only

e It is planned that testing will comprise an antigen test performed at screening and on Day -1 prior to admission to the clinical unit. The definition of the COVID-19 testing time points are subject to change based on the current risk mitigation in place and will be agreed by the study team and documented in the ISF via the Clinical Kick-Off Meeting minutes.

f Participants will be randomised on the morning of Day 1 prior to dosing

g Participants will receive a dose of MMV367 or placebo in the morning on Days 1, 2 and 3

h Targeted (symptom driven) physical examination of the relevant body system(s) as clinically indicated, as per the investigator's judgement

i Haematology, coagulation, clinical chemistry and urinalysis at each time point, including virology and FSH (post-menopausal female participants only) at screening.

j Post-menopausal female participants only

k All female participants

l See [Appendix 6](#) for single and triplicate 12-lead ECG time points. For triplicate ECGs, participants will be required to rest in the supine position with no external stimuli (e.g. music or television) for 15 min prior to the nominal time point where a triplicate ECG is scheduled.

m Continuous Holter monitoring will commence at least 1.5 h prior to dosing until at least 24 h post-dose. Participants will be required to rest in the supine position with no external stimuli (e.g. music or television) for 15 min prior to the nominal time point where an ECG extraction is scheduled. See [Appendix 6](#) for Holter extraction time points.

n Blood pressure, heart rate and respiratory rate at all time points. Oral temperature will be measured at screening and admission only. See [Appendix 6](#) for vital signs and orthostatic vital signs time points.

o See [Appendix 6](#) for PK sample time points.

p Sample will be taken prior to IMP administration (≤2 h before dosing).

**Appendix 5      Part 1 (All Cohorts) Safety and Pharmacokinetic Assessment Time Points  
(Days 1 to 7)**

Study Day	Time point	Plasma PK	Urine PK a	Safety Labs and Urinalysis	Holter Extractions	Vital Signs b	Orthostatic Vital Signs	Single 12-lead ECGs	Triplicate 12-lead ECGs
1	-1.5 h				X			X	
	-1 h				X			X	
	Pre-dose (-0.5 h)	X	X		X	X	X	X	
	0 h		0 to 6 h						
	0.5 h	X			X	X		X	
	1 h	X			X			X	
	2 h	X			X	X	X	X	
	3 h	X			X			X	
	4 h	X			X	X	X	X	
	5 h	X						X	
	6 h	X	6 to 12 h		X	X		X	
	8 h	X			X	X		X	
	10 h					X			
	12 h	X	12 to 24 h		X	X	X	X	
2	24 h	X	24 to 48 h	X	X	X	X		
3	48 h	X	48 to 72 h			X			X
4	72 h	X				X			X
5	96 h	X		X		X			X
7	144 h	X		X		X	X		X

a Part 1, Cohorts 1C and 1D only.

b Blood pressure, heart rate and respiratory rate at all time points.

Allowable windows for PK blood sampling, vital signs assessments and ECGs can be found in: [Sections 13.1, 14.6 and 14.7](#).

**Sponsor/Quotient Sciences Confidential****Appendix 6      Part 2 Safety and Pharmacokinetic Assessment Time Points (Days 1 to 14)**

Study Day	Time point	Plasma PK	Safety Labs and Urinalysis	Holter Extractions	Vital Signs a	Single 12-lead ECGs	Triplicate 12-lead ECGs
1	-1.5 h			X		X	
	-1 h			X		X	
	Pre-dose (-0.5 h)	X		X	X	X	
	0 h						
	0.5 h	X		X	X	X	
	1 h	X		X		X	
	2 h	X		X	X	X	
	3 h	X		X		X	
	4 h	X		X	X	X	
	5 h	X					
	6 h	X		X	X	X	
	7 h						
	8 h	X		X	X	X	
	10 h				X		
	12 h	X		X	X	X	
2	24 h	X	X	X	X	X	
3	48 h	X			X		X
4	72 h	X			X		X
5	96 h	X	X		X		X
7	144 h	X	X		X		X
8	-1.5 h			X		X	
	-1 h			X		X	
	Pre-dose (-0.5 h)	X		X	X	X	
	0 h						
	0.5 h	X		X	X	X	
	1 h	X		X		X	
	2 h	X		X	X	X	
	3 h	X		X		X	
	4 h	X		X	X	X	
	5 h	X					
	6 h	X		X	X	X	
	7 h						

**Sponsor/Quotient Sciences Confidential**

Study Day	Time point	Plasma PK	Safety Labs and Urinalysis	Holter Extractions	Vital Signs a	Single 12-lead ECGs	Triplicate 12-lead ECGs
	8 h	X		X	X	X	
	10 h				X		
	12 h	X		X	X	X	
9	24 h	X		X	X	X	
10	48 h	X	X		X		X
11	72 h	X			X		X
12	96 h	X	X		X		X
14	144 h	X	X		X		X

a Blood pressure, heart rate and respiratory rate at all time points.

Allowable windows for PK blood sampling, vital signs assessments and ECGs can be found in: [Sections 13.1, 14.6 and 14.7](#).

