#### **14.5.1 Haematology, Clinical Chemistry and Coagulation**

Laboratory tests will be performed by The Doctors Laboratory according to the time schedules presented in [Appendix 5](#), [Appendix 6](#) and [Appendix 7](#). Blood samples will be collected and processed as detailed in the CSPM. Scheduled blood samples will be taken following an 8 h fast.

The acceptable deviations from the nominal blood sampling time points for laboratory assessments are:

- Post-dose/post-first dose blood samples will be taken  $\pm$  1 h from the nominal blood sampling time
- End of Study blood samples will be taken  $\pm$  1 day from the nominal blood sampling time

Creatinine clearance (CLcr) will be calculated at admission by The Doctors Laboratory using the Cockcroft-Gault equation [\[10\]](#) and body weight. Results of this assessment will be used for PK analysis and PK-PD modelling (reported separately).

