#### **14.5.2 Urinalysis**

Urinalysis will be performed on-site using a dipstick according to the time schedules presented in [Appendix 2](#), [Appendix 3](#) and [Appendix 4](#).

Urine samples will be collected and processed as detailed in the CSPM.

In Part 1, any urine used for urinalysis will be added back to the full sample for PK and metabolite identification analysis. If microscopy is required, a urine sample (approximately 20 mL) will be taken from the urine PK and metabolite collection, and sent to The Doctor's Laboratory, after the void has been weighed.

In Parts 2 and 3, if microscopy is required, a urine sample will be sent to The Doctor's Laboratory.

The acceptable deviations from the nominal urine sampling time points for urinalysis are:

- On Day 3 (Part 3 only): the pre-dose urine sample will be taken  $\leq$  1 h before dosing.
- Post-dose urine samples will be taken  $\pm$  2 h from the nominal urine sampling time
- End of Study urine samples will be taken  $\pm$  1 day from the nominal urine sampling time

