### **3 Introduction**

This document details the following for Quotient Sciences (Quotient) Study QSC207031 (MMV\_MMV367\_21\_01):

- Criteria to be used for the definition of the populations and analysis sets relating to safety, taste and pharmacokinetic (PK) data
- Handling of missing data
- Proposed tables, figures and data listings (TFLs) for demographic, dosing, safety and PK data
- Methods for PK parameter estimation and the formal statistical analysis

This document has been compiled according to the Quotient standard operating procedure (SOP) "Production of Reporting and Analysis Plans" and has been written based on information contained in the final study protocol (v3.0) dated 08 Sep 2022.

The v1.0 RAP was amended to incorporate updates from the v3.0 protocol, which included increasing the window of the end of study visit in each study part, from  $\pm 1$  h to  $\pm 1$  day. Thus, ensuring sufficient time to complete all agreed procedures. Furthermore, additional clarification relating to the collection of urine for PK assessments has also been included.

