#### **11.4 Laboratory Evaluations**

The details of sample collection for laboratory safety analysis are described in the study protocol.

Where a value is provided by the safety laboratory as either above or below the limit of detection (LOD) this will be set to the respective LOD itself for descriptive summaries. No imputations will be made in the individual listings.

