##### **11.4.1 Summary Tables for Laboratory Evaluations**

For each study part, haematology, coagulation and clinical chemistry data will be summarised (n, mean, SD, median, minimum and maximum) for each laboratory parameter at each time point, including changes from baseline (Admission, Day-1) at each scheduled post-baseline time point by treatment in Part 2, and by all placebo, all active and each dose level in Part 1 and Part 3.

Shift tables from baseline to each scheduled post-baseline time point (with respect to the number and percentage of subjects with values below, within or above the reference range) will be presented by treatment in Part 2, and by all placebo, all active and each dose level in Part 1 and Part 3. Percentages will be based on the number of subjects with measurements at baseline and the relevant post-baseline time point.

For fasting-sensitive laboratory parameters (i.e., glucose) results taken in the non-fasted state (i.e., LBFAST=N) will not be included in summary statistics by time point or be used in derivations of changes from baseline. For tabulations (e.g., shift tables) both fasted and non-fasted results will be pooled and used in the tabulations, using the appropriate fasted or non-fasted reference range. All results (fasted or non-fasted) will be listed with non-fasted data flagged.

Reference ranges for each laboratory parameter will be presented for the relevant parameter in each summary table.

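### Part 2 safety bloods: protocol Appendix 6 sets the first post-dose draw at 24 h in Period 1 but 48 h in Period 2, while SAP Appendix 5 sets 24 h in both periods

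*Protocol*

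**What the plan says.** For blood tests, protocol Section 14.5.1 hands the timing to the time-point tables: "Laboratory tests will be performed by The Doctors Laboratory according to the time schedules presented in" Appendices 5, 6 and 7. Appendix 6 is the one for Part 2. The permitted deviation after dosing is plus or minus "1 h from the nominal blood sampling time", with a one-day allowance at the end-of-study visit.

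In protocol Appendix 6 the column headed "Safety Labs and Urinalysis" is marked on Days 2, 5 and 7 after the Day 1 dose (24, 96 and 144 h). After the Day 8 dose it is marked on Days 10, 12 and 14 (48, 96 and 144 h), and the Day 9 cell is empty. In SAP Appendix 5 the same column is marked on Days 2, 5 and 7 and then on Days 9, 12 and 14, and the Day 10 cell is empty.

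The SAP Introduction states that the document "has been written based on information contained in the final study protocol (v3.0) dated 08 Sep 2022", and SAP Section 13.2 declares no changes to the planned analyses. SAP Section 3.2.3 points to its own Appendix 5 for the Part 2 time points, but SAP Section 11.4 says: "The details of sample collection for laboratory safety analysis are described in the study protocol". SAP Section 11.4.1 then summarises results, changes from baseline and shifts "at each scheduled post-baseline time point by treatment in Part 2".

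**The concern.** Part 2 is a two-period crossover in which each participant takes the same dose once fed and once fasted. If the first blood draw falls at 24 h in one period and 48 h in the other, nominal time is tied to period. A 24 h row of a by-treatment table can then hold only Period 1 data, and a 48 h row only Period 2 data. Within either row the fed and fasted columns come from different people, although the design would allow the same people in both.

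The two documents also give different instructions for the same day. A site following the protocol takes no blood on Day 9, and one following the SAP appendix would depart from the protocol. Change from baseline in laboratory tests is part of the primary endpoint (protocol Section 7). Protocol Section 6.2 expects food may raise exposure, yet participants who are fed in Period 2 have no scheduled 24 h blood test after that dose.

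**Working it through.** **1. Are the marks read correctly?** Each row used has six cells for the six assessment columns (plasma PK, labs, Holter, vital signs, single ECG, triplicate ECG). In the disputed rows every other mark agrees between the documents and with Period 1: Holter and single ECG at 24 h, triplicate ECG at 48 h. Only the lab mark moves.

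| Post-dose safety bloods | Period 1 | Period 2 |
|---|---|---|
| Protocol Appendix 6 | 24, 96, 144 h | 48, 96, 144 h |
| SAP Appendix 5 | 24, 96, 144 h | 24, 96, 144 h |

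**2. Can a 48 h draw count as the 24 h draw?** No. The two are 24 h apart and the window is 1 h either side.

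**3. How much of the schedule is affected?** There are 3 draws in each of 2 periods, so 6 per participant. With 8 participants that is 8 × 6 = 48 draws. The documents disagree on one per participant: 8 of 48 = 16.7%.

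**4. What do the table rows hold?** Assume 8 participants complete both periods, 4 per sequence. The documents say balanced; 4 and 4 is inferred from that.

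| Row | Protocol: fasted / fed / in both | SAP: fasted / fed / in both |
|---|---|---|
| 24 h | 4 / 4 / 0 | 8 / 8 / 8 |
| 48 h | 4 / 4 / 0 | none |
| 96 h | 8 / 8 / 8 | 8 / 8 / 8 |
| 144 h | 8 / 8 / 8 | 8 / 8 / 8 |

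Under the protocol, the 4 fasted values at 24 h come from the fasted-then-fed sequence and the 4 fed values from the other sequence. At 48 h the sequences swap.

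**5. What if participants drop out after Period 1?** Laboratory tables use the safety analysis set, which keeps anyone who received any study drug (SAP Sections 6.1 and 11). Suppose 8 are dosed, 2 leave after Period 1 and neither is replaced. The 24 h row still holds 4 + 4 = 8. The 48 h row falls to 6, split 4 fasted and 2 fed, 3 and 3, or 2 and 4, depending on which sequence loses people. Nobody appears under both treatments in either row.

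**6. Do the other parts show the intention?** Part 1 (protocol Appendix 5) uses 24, 96 and 144 h. Part 3 (protocol Appendix 7) uses 48, 96 and 144 h after its final dose. It also uses 48 h after its first dose, because the Day 3 pre-dose lab is labelled as the Day 1 48 h sample. So Part 1 is 24 h throughout, Part 3 is 48 h throughout, and only Part 2 mixes the two.

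**The case against.** The strongest reply is that the operative time is stated. Section 14.5.1 makes Appendix 6 govern, the SAP defers to the protocol for collection, and staff would draw at 48 h in Period 2. Part 3 shows that a 48 h draw after a final dose is an accepted pattern. On that view the only defect is one mark in a SAP appendix. The first half stands: read literally, the protocol means 48 h. The Part 3 analogy is weak, since Part 3 uses 48 h after its first dose too. Correcting only the SAP mark would make the documents agree but would leave the two periods sampled at different times.

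It can also be said that the protocol already tolerates unequal timing, since the Period 2 144 h draw falls at the end-of-study visit with its one-day window. That is true. But the nominal time there is still 144 h, so both periods land in the same table row.

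The point that the harm is small stands. No paired laboratory comparison or test is planned, and change from baseline is taken within participant. Participants stay in the unit until Day 12, with vital signs and ECGs at both 24 h and 48 h. Extra safety bloods are allowed (protocol Section 14.13), and safety time points can be changed during the study (Section 8.2.1). These are discretionary powers; they do not reconcile the two schedules.

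A reader might go further in four ways that the documents do not support:

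- **The protocol mark is a proven slip.** A slip is the likelier explanation, but no text states the intended time.
- **The SAP tables require a Day 9 row.** The Part 2 laboratory shells use only generic time-point labels.
- **Dropout shrinks both rows.** It shrinks only the 48 h row (step 5). The rule restricting analysis to completers belongs to the pharmacokinetic food-effect model in SAP Section 9.6.2.
- **Urinalysis is affected in the same way.** Despite the shared column, Section 14.5.2 says "Urinalysis will be performed on-site using a dipstick according to the time schedules presented in" Appendices 2, 3 and 4. The lab and urinalysis rows of protocol Appendix 3, as available for this review, have more cells than visit columns and cannot be read reliably.

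**Conclusion.** The inconsistency is real, lies in the current text of both documents, and is minor. Protocol Appendix 6 and SAP Appendix 5 disagree on one blood draw per participant in Part 2, and the protocol's own two periods differ without explanation. With 8 completers and an assumed 4 per sequence, the cost under the protocol is an unpaired 4 against 4 at each of 24 h and 48 h, where the SAP schedule would give a fully paired 8 against 8 at 24 h. There is also no scheduled 24 h blood after the second dose.

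A reader might infer that the food-effect conclusion is at risk. It is not: that analysis uses plasma concentrations, whose sampling times match in both periods, and no formal test uses laboratory data. Confidence is high that the marks differ. That 24 h was meant in both periods is an inference.

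**What to change.** In protocol Appendix 6, move the Period 2 lab mark from Day 10 (48 h) to Day 9 (24 h). This matches Period 1 and SAP Appendix 5, which then needs no change. Check that the safety-lab and urinalysis rows of protocol Appendix 3 agree. The number of draws stays at 6 per participant, 48 for 8. The cost is a protocol amendment agreed and documented under Section 17.1. Version 3.0 corrected other schedule appendices under a non-substantial amendment; the sponsor would have to classify this one.

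If 48 h is truly intended, schedule it in both periods and amend SAP Appendix 5 as well. Replacing 24 h by 48 h in both periods keeps 48 draws. Taking both times in both periods means 8 draws per participant, 8 × 8 = 64 in total, or 16 more.

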## Sponsor/Quotient Sciences Confidential

## Appendix 7 Part 3 Safety and Pharmacokinetic Assessment Time Points (Days 1 to 9)

Study Day	Time point	Plasma PK	Safety Labs and Urinalysis	Holter Extractions	Vital Signs a	Orthostatic Vital Signs	Single 12-lead ECGs	TriPLICATE 12-lead ECGs
1	-1.5 h			X			X	
	-1 h			X			X	
	Pre-dose (-0.5 h)	X		X	X	X	X	
	0 h							
	0.5 h	X		X				
	1 h	X		X	X		X	
	2 h	X		X	X	X	X	
	3 h	X		X	X		X	
	4 h	X		X	X	X	X	
	5 h	X						
	6 h	X		X	X	X	X	
	8 h	X		X	X		X	
	10 h			X	X			
	11 h							
	12 h	X		X	X	X	X	
2	-1.5 h							X
	-1 h							X
	Pre-dose (-0.5 h) b	X		X (Day 1, 24 h)	X	X (Day 1, 24 h)		X
	0 h							
	1 h							
	2 h							
	3 h							
	4 h	X			X			X
	5 h							
	6 h	X			X			X
	7 h							
	8 h							
	9 h							
	10 h				X			
	11 h							
	12 h	X			X			X
3	-1.5 h			X			X	
	-1 h			X			X	
	Pre-dose (-0.5 h) c	X	X (Day 1, 48 h)	X (Day 1, 48 h)	X	X	X	

## Sponsor/Quotient Sciences Confidential

Study Day	Time point	Plasma PK	Safety Labs and Urinalysis	Holter Extractions	Vital Signs a	Orthostatic Vital Signs	Single 12-lead ECGs	Triplicate 12-lead ECGs
	0 h							
	0.5 h	X		X	X		X	
	1 h	X		X	X		X	
	2 h	X		X	X	X	X	
	3 h	X		X	X		X	
	4 h	X		X	X	X	X	
	5 h	X						
	6 h	X		X	X	X	X	
	7 h							
	8 h	X		X	X		X	
	9 h							
	10 h			X	X			
	11 h			X				
	12 h	X		X	X	X	X	
4	24 h	X		X	X	X	X	
	36 h	X			X			X
5	48 h	X	X		X			X
6	72 h	X			X			X
7	96 h	X	X		X			X
9	144 h	X	X		X	X		X

a Blood pressure, heart rate and respiratory rate at all time points.

b 24 h post-dose Day 1 sample will be taken pre-dose on Day 2

c 24 h post-dose Day 2 sample will be taken pre-dose on Day 3

Allowable windows for PK blood sampling, vital signs assessments and ECGs can be found in: [Sections 13.1, 14.6 and 14.7](#).

**Sponsor/Quotient Sciences Confidential**

---

**Appendix 8      Breakfast Content (Part 2 only)**

Meal Description	Energy from Fat (%)	Composition
High-Fat Breakfast (FDA approved) a	57.90	1 (40 g) hash brown, 2 (80 g) smoked rindless streaky bacon, 1 medium (45 g) egg fried in 10 g of butter, 2 slices (95 g) of white sliced bread with 20 g of butter, 240 mL of full fat milk

Values/content are approximate. Every effort will be made to include the items described above; however, items may be replaced as long as they contain the equivalent nutritional content as the item it has replaced.

aFor FDA high-fat breakfast, if a replacement item is required it will be of comparable volume and viscosity.

